iMpact of therapeUtic live muSic on pain and
distress levels during Interventions within the
paediatricC Emergency Department

Research Protocol

Version: V8.3

Date: 13/11/2018

Study Title:

Music:ED

iMpact of therapeUtic live muSic on pain and distress during Interventions within the
paediatric Emergency Department.

Project Team

The core project team will consist of

[name] - Consultant in Paediatric Emergency Medicine, (PI)

[name] CPsychol. - University of Liverpool Lead Applicant

[name] - Lead Musician, Director of Cascade Music

[name] – Musician, Cascade Music

[name] - Consultant in Paediatric Emergency Medicine

[name] - Research Nurse

[name] - Research Nurse

The researchers have relevant methodological, clinical and academic expertise and will share particular facets of their expertise. All listed above have current GCP certification.

Introduction and Context

The Emergency Department (ED) can be stressful and traumatic, especially for children and young people, and the clinical environment can be a frightening, unfamiliar space, which adds to an already anxious experience.

Musicians from Cascade Music, who have an established track record of working with the Paediatric ED, will provide recruited participants in the experimental arm with high-quality calming, distracting music during selected procedures. A wide range of music will be used, ranging from nursery rhymes to classical to pop tunes, to engage with and comfort children, taking their attention away from their immediate pain or distress. Pain scores throughout the procedure will be self-assessed by patients (if old enough to use a self assessment tool i.e. 3 years and above) as well as observed by a Research Nurse. Qualitative data on distress and the experiences of patients, families and staff will also be collected via a questionnaire. Participants recruited to the control arm will complete the same measures but receive no live music.

This project is underpinned by three areas of need:

1. Despite there being a wide breadth of clinical studies that have used music within various healthcare settings, one area that has been almost completely unexplored is the Paediatric Emergency Department (PED). Alder Hey Children's Hospital (AHCH), as a world leader in research, is ideally situated to conduct this preliminary research.
2. By 2020 AHCH plans to be a world class, child-focused centre of research, innovation and education expertise to improve the health and wellbeing outcomes for children and young people. Supporting patients through stressful and invasive procedures is crucial. Inspired by the patients and families that we care for, this research fits well with the AHCH vision, demonstrating an innovative and evidence-informed approach to enhancing practice.
3. The University of Liverpool's impact intensive approach to research is a key strength. This study is designed to have a positive immediate impact on the children and young people participating and those undergoing interventional procedures in the future, helping to enhance patient experience of the ED.

Value of the study

There is a growing evidence-base for the use of music in healthcare settings, with music already demonstrated to reduce stress, distress and the perception of pain in some clinical contexts^{1 2}. Yet, there is a lack of studies examining the impact of live music in paediatric emergency contexts.

A literature review revealed that there is a lack of studies examining the impact of live music in paediatric emergency contexts.

Related studies either used recorded music in the place of live music, or, if live music was used, then it was within a non-emergency setting.

Prior related studies include:

*'Interactive music as a treatment for pain and stress in children during venipuncture: a randomized prospective study.'*³

This controlled study demonstrates that songs and music, performed by "professional" musicians, have a beneficial effect in reducing distress before, during, and after blood tests. This study shows, moreover, that the presence of musicians has a minor, but yet significant, effect on pain due to needle insertion.'

This study uses similar methods and looked for similar outcomes as Music:ED, but in a non-emergency setting

*'Music to reduce pain and distress in the pediatric emergency department: a randomized clinical trial.'*⁴

Health care providers reported that it was easier to perform the procedure for children in the music group (76% very easy) vs the standard care group (38% very easy) (P = .03). Health care providers were more satisfied with the intravenous placement in the music group (86% very satisfied) compared with the standard care group (48%) (P = .02).

Music may have a positive impact on pain and distress for children undergoing intravenous placement. Benefits were also observed for the parents and health care providers.

This study uses similar methods and looked for similar outcomes as Music:Ed, but using recorded rather than live music, and in a non-emergency setting.

The Music:ED study will therefore use a controlled experimental design to investigate the impact of using therapeutic live music in the Alder Hey Paediatric Emergency Department to reduce pain and distress during interventional procedures.

The outcomes of the study will provide evidence for the use of live music in the PED to support and enhance patient experience. Distress is often particularly high within the emergency department. If a patient's experience whilst attending the Emergency Department can be less traumatic, this will be of benefit to all: patients, families and clinicians. A patient who is less distressed is more cooperative and may be easier and quicker to treat.

Methodology and Methods

Research Question

Does live music decrease the pain and distress of patients undergoing a procedure within the paediatric emergency department?

Aims of the Study

Our aims/objectives include:

1. To explore whether live music helps to decrease pain and distress in patients in the Paediatric Emergency Department
2. To explore whether procedures can be carried out with greater ease from a clinician's perspective and whether staff experience of the situation is impacted by the presence of live music.
3. Exploring the overall impact on the ED experience from the patients, families and clinicians' perspectives.

Methodological Approach

We have chosen a mixed method design to provide us with different forms of data and insights from multiple practitioner, parent and patient perspectives throughout the experience.

Quantitative data includes collecting information about the patient's pain levels and qualitative data will be collected from open response questionnaires to explore patient distress and the practitioner, parent and patient perspectives on the experience.

Methods

There will be an experimental (live music) and a control (no live music) group.

Research Nurses will identify appropriate patients using a screening tool that will outline the inclusion/exclusion criteria. Participant Information Sheets (PIS) will be provided to patients and their families for their appropriate ages. They will be offered a copy of the results if they would like and will be told how the results will be reported when the study is completed.

After gaining written consent from the parent and written or verbal assent from the child, Wong-Baker pain scoring methods will be explained in advance of the procedure. Necessary data will be collected for the CRF.

The participant's involvement in the study will be limited to the length of time of their Emergency Department visit, so will be just one day and one procedure.

For the experimental (music) group, Cascade's musicians will spend eight weeks, twelve hours per week in the ED and will aim to recruit all eligible children during that period. As this is a pilot study recruitment targets need to remain flexible, but are estimated at 60-80 participants (per group).

The same number of participants will be recruited to the control (no live music) group as a comparison, on days that the musicians are not in the department. All patients in both groups will continue to receive standard care. Each child can only be in the study once and for one procedure. Patients will be free to withdraw from the study at any time.

Following the procedure and interviews, patients involved will be offered a sticker and a CD of calming music recorded by Cascade Music as a thank you for their participation. For ethical reasons, this will not be mentioned in advance.

Timeline:

December 2018:

Implementation of study including finalising ethical approval

Recruitment of Research Nurse,

Publicise study within Alder Hey Children's Hospital's Emergency Department.

January - March 2019:

Recruitment of participants to the study, both experimental (music) and control (non-music) groups.

Data collection from participants.

March - May 2019:

Complete data analysis

Write report

Explore dissemination options including publishing and conferences

Plan next funding application

Methods of data collection and analysis

Three sets of data will be collected:

1. Quantitative: Self-reported pain.

A validated observational tool will be used: Wong Baker Faces.

This is suitable for children age 3+. As children self-report, the Research Nurse will collect this data on a paper CRF. Wong Baker scores will be collected before, during and after the procedure. If mid-procedure collection of pain score is inappropriate, then participants can be asked about mid-procedure pain scores after the procedure.

A self-reported pain score will also be taken in advance, during the recruitment process, to provide a baseline measure.

2. Quantitative: Observed pain.

Data will be collected on observed pain levels using a validated observational tool: Faces, Legs, Activity, Cry and Consolability (FLACC) pain assessment tool.

This tool is suitable and validated for all ages of the recruited participants, from 6 months until 16 years. References regarding justification of this scale for these age ranges are below.^{5 6}

Scoring will take place before, during and after the procedure.

The Research Nurse will carry out this scoring, and when available, an independent observer from the Emergency Department staff will also. The Research Nurse will collect this data on the paper CRF.

Heart rate will also be monitored throughout, where a child is cooperative enough. HR will be noted approximately every two minutes before, during and after procedure, (cleaning marks the beginning of the procedure, final bandage/dressing marks the completion). The Research Nurse will note HR data on the CRF. There will be an option for the Research Nurse to record 'not available' for heart rate measurements either because child refuses or because of probe or monitor issues etc.

3. Qualitative: Distress and experiences of patients, families and clinicians.

Our outcome measures will include collecting qualitative information on patient's distress, and patients', families' and clinician's Emergency Department experience. All recruited patients will receive a paper questionnaire with open text response options.

Qualitative questions for Experimental AND Control Groups:

The following two questions will be asked of both the experimental (live music) AND control (no live music) groups. The questions will be asked of each of these two people: patient and parent/legal guardian.

'Please answer the following questions, in particular, in regard to distress levels/lack of distress':

- Qualitative question 1. What do you think helped you/your child during their procedure?

- Qualitative question 2. Did anything make the situation worse?

Qualitative questions for Experimental Group Only:

Within the experimental group only, the following three additional questions will be asked, via a paper questionnaire, of each of these three people: patient, parent/legal guardian and clinician. These questions directly link to the objectives of the study.

These questions are in particular regard to music, which is why they would not be appropriate to be asked of the control (no live music) group.

- Qualitative Question 1. How did you feel the music affected the child's distress before, during and after the procedure?

- Qualitative Question 2. Can you tell me about how the live music helped or hindered the procedure?

- Qualitative Question 3. Can you tell me about your experience of the ED (Emergency Department) today, in particular in regard to the music?

The qualitative questions will be included in a open ended questionnaire style sheet which the parent, child or practitioner if the parent wishes, can fill out between the end of the music intervention and when they are discharged from the ward. It will be collected by the RN and stored in a secure room in a locked filing cabinet.

Target population and sampling

This will be a single centre study.

Study participants for both the control and experimental groups of the study will be recruited from AHCH Emergency Department. The study population will consist of children between the age of 6 months and 16 years needing to undergo a painful procedure from a specified list. The Research Nurse will use a screening tool to assess eligibility within this age group.

Necessary data will be collected for the CRF by the Research Nurse:

CRF:

Patient's name

Patient's age

Patient's gender

Parent(s)/legal guardian in attendance during procedure (names)

Whether or not the patient has had this procedure before

How many times the child has visited the hospital in the last 12 months

Have they had an upsetting hospital experience in the past? Yes or no

Record a Wong-Baker pain score at this point (for children age 3+) as a baseline measure

Record whether patient has had analgesia in advance, or during hospital visit

Record use of local anaesthetics e.g EMLA/amecop, LAT gel, cold spray (ethyl chloride)

Record use of Entonox during the procedure

Record if other distraction methods were also used

(Play Specialist/books/bubbles/IPad/TV/ iPhone/ staff dancing and singing, etc)

Record whether the procedure was successful

Record the duration of the procedure (cleaning marks the beginning of the procedure, final bandage/dressing marks the completion)

Record how many attempts were required to carry out procedure

Record the role and grade of the Clinician carrying out the procedure

Record heart rate at 2-minute intervals if tolerated. Include option for the research nurse to record 'not available' for heart rate measurements either because child refuses or if probe or monitor issues etc

Is there an independent observer present? If so, who?

Inclusion criteria

Parent/Legal Guardian present and able to consent.

Age range: 6 months - 16 years. (see references at end notes 5&6 below)

Procedures: Capillary blood sampling, cannulation, venepuncture, suturing, wound cleaning and closure.

Families and children whose primary language is other than English will be included in the study if their English speaking skills are at a level that they can understand and complete the consent/assent process.

Exclusion criteria

Children with Special Educational Needs, children with global development delay, sensory impairments, neurological deficits or disorders, impairment to pain i.e. spina bifida.

Children in resuscitation or unconscious.

Non-English speaking.

Suspected ingestion of recreational drugs, antidepressants or alcohol

Concerns relating to NAI (non accidental injury)/safeguarding concerns

Life or limb critical injuries

Children too unwell to participate

Recruitment

Research Nurses will identify appropriate patients using a screening tool that will outline the inclusion/exclusion criteria. For inclusion in either group, a parent or legal guardian must be available to give consent, collected by the Research Nurse.

The Research Nurse will introduce the study to potential recruits, and supply and explain Participant Information Sheets. Posters will be displayed within Alder Hey's Emergency Department to promote the study and give some initial details.

The same number of participants will be recruited to the control (no live music) group as a comparison, on days that the musicians are not in the department. All patients in both groups will continue to receive standard care. Each child can only be in the study once and for one procedure. Patients will be free to withdraw from the study at any time.

Ethics and governance

Full ethics approval will be obtained and clear data protection measures will be put in place for sharing of data between the research team. Parental consent and children's assent will be obtained in all cases. Consent and assent will specifically address the use of quotations in papers, conferences and dissemination.

We do not expect that the study will raise significant issues and will be of minimal risk to the children (and their families). The main issues relate to the engagement of children within research and ensuring that they understand what they are assenting to and are able to indicate (at any point) if they wish to withdraw from the study.

Data Protection

Alder Hey Children's Hospital, as the study sponsor, will own the study data.

The researchers will comply with the requirements of the Data Protection Act. Storage and anonymity: Research nurses will collect data from parents and children and enter them into the database. Data will be anonymised and will be stored electronically on Alder Hey Children's NHS Foundation Trust's secure server. This can be accessed when on trust premises. The data will NOT be shared with other organisations other than members of the study team which includes the University of Liverpool, or exported outside the EU. Consent forms will be kept separately from the data. Information about participants will not be disclosed to anyone. Any identifying information will be changed to maintain anonymity and the data will be stored securely. After storage (10 years), data will be deleted from the AHCFT secure server. Any paper based information such as consent forms will be destroyed.

The researchers will comply with the requirements of the Data Protection Act. This will be achieved through careful and conscientious management of the study including approaching the families, handling the data and through to dissemination of the findings. Only the Research Nurse, PI and treating clinician will access to the child's medical or other records. All data will be encrypted. All electronic files will be encrypted. Reports from and presentations from the study will not contain any quotes directly attributable to individuals and so will be anonymized. Any specific contextual information will be omitted to ensure that participants' identities are not disclosed. This will be made very clear in the information sheet and within the consent/assent forms.

Data Analysis

Quantitative data will be entered into SPSS. We will analyse the data using the chi-square test for trend, paired samples t-tests and Wilcoxon sign ranks tests as appropriate. Participants with missing data (either before procedure or after procedure) will be excluded from analysis. NVivo 10 Software will be used to assist in the organization and coding of qualitative data (e.g. free text open question responses). Qualitative thematic analysis will be interpretive and iterative. Our approach to synthesizing qualitative and quantitative data will draw on the constant comparative method.

Dissemination

Findings from the study will be disseminated to professionals and to children and their families. Dissemination potentially includes publication in journals and via presentation at conferences and at practice development workshops. This will be done locally through the associated universities and hospitals as well as potentially internationally. By working with colleagues in clinical practice on an on-going basis throughout the study, the researchers anticipate that the study will have a direct impact on practice.

Benefit to patients

Findings will be used to further our understanding of the potential benefits of using live music within the Paediatric Emergency Department, with an aim to improve patient experience.

Link to Alder Hey Research & Universities' Strategies

Alder Hey Children's Hospital's strategy is to build a healthier future for children and young people. One of Alder Hey's main aims is to 'ensure all of our patients and their families have a positive experience whilst in our care'. This study very much follows this ethos, by exploring ways to make the hospital experience a less traumatic one.

A key strength of the University of Liverpool's research strategy is its impact intensive approach. The design of this study will explore ways of making immediate, effective improvements to the care of children and young people.

References:

¹ A. Y. R. Kühlmann(2018) *Meta - analysis evaluating music interventions for anxiety and pain in surgery*. Available at 002 <https://onlinelibrary.wiley.com/doi/abs/10.1/bjs.10853>

² Kari Sand-Jecklin, EdD, MSN, RN, AHN-BC, Howard Emerson, BA, CMP (2010) *The Impact of a Live Therapeutic Music Intervention on Patients' Experience of Pain, Anxiety, and Muscle Tension* *Holist Nurs Pract* 2010;24(1):7–15

³ *J Dev Behav Pediatr.* 2007 Oct;28(5):399-403.

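### The protocol names no main pain measure, time point or music-versus-control comparison, so nothing fixes in advance which result answers its research question

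*Protocol*

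**What the plan says.** The Research Question section asks: "Does live music decrease the pain and distress of patients undergoing a procedure within the paediatric emergency department". The first item under Aims of the Study is softer: "To explore whether live music helps to decrease pain and distress". The Value of the study section is firmer again: "The outcomes of the study will provide evidence for the use of live music in the PED".

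Methods of data collection and analysis describes the numerical data:

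- **Wong-Baker**, self-reported, age 3 and over: before, during and after the procedure, plus a baseline score at recruitment. The mid-procedure score may be asked for afterwards.
- **FLACC**, observed, described as suitable for every recruited age: "Scoring will take place before, during and after the procedure". The research nurse scores it, joined by an independent observer when one is available.
- **Heart rate**, an addition under observed pain: about every two minutes across the same three phases, where the child tolerates it.

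Distress is assigned to open-text questionnaires, not to any of these scores.

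The Data Analysis section plans the "chi-square test for trend, paired samples t-tests and Wilcoxon sign ranks tests as appropriate". It ties none of these tests to a measure, a time point or a contrast. Its only mention of time points is the rule that excludes participants whose before or after data are missing. No section names a primary outcome or states a significance level. The Methods section calls the study a pilot with an estimated 60 to 80 participants per group.

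**The concern.** A question of the form *does music decrease pain* needs one result that is agreed beforehand to answer it. Here several could be put forward, and the hints in the protocol point different ways. The study title concerns pain during interventions, but the missing-data rule mentions only before and after. Two of the three listed tests are paired, so they compare time points within a group and not music with control.

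If the choice is made once scores are visible, any single favourable p-value can be presented as the answer. The team knows which children had music, so a choice made then could not be shown to be independent of the results. Adjustment for multiple testing can reasonably sit in an SAP. Which outcome answers the research question is normally settled in the protocol.

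**Working it through.** The protocol gives no error rate or power figure, so there is nothing of its own to reproduce. The check asks how far the chance of a false positive rises under plausible readings.

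**Inputs**

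- Measures: 3 (Wong-Baker, FLACC, heart rate). Phases: 3 (before, during, after). Both come from Methods of data collection and analysis.
- Significance level: not stated; two-sided α = 0.05 assumed.
- Number of tests k: not stated. Three counts are assumed: 9 (3 measures × 3 phases); 6 (3 measures, during and after only, as would apply if the before-procedure scores precede the music); 4 (two pain scales, during and after). Heart rate is reduced to one value per phase.
- Correlation ρ between test statistics: not stated; 0 to 0.9 assumed.

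The recruitment Wong-Baker score is left out. It is a baseline, and a group difference there would show imbalance, not an effect of music.

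**Step 1, independent tests.** P(at least one p < 0.05 with no true effect) = 1 − (1 − α)^k.

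- k = 9: 1 − 0.95^9 = 1 − 0.630 = 0.370
- k = 6: 1 − 0.95^6 = 1 − 0.735 = 0.265
- k = 4: 1 − 0.95^4 = 1 − 0.8145 = 0.1855

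**Step 2, correlated tests.** Multivariate normal simulation, 400,000 draws:

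| Comparisons | ρ = 0 | ρ = 0.5 | ρ = 0.9 |
|---|---|---|---|
| 9 | 37.0% | 27.0% | 12.3% |
| 6 | 26.5% | 20.7% | 10.8% |
| 4 | 18.5% | 16.1% | 9.9% |

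For nine comparisons the values at ρ = 0.3 and 0.7 are 32.6% and 20.3%. The rows for 9 and 6 use one common correlation. The row for 4 sets the correlation between measures and between times separately, so pairs that differ in both have the product (0.9 × 0.9 = 0.81). With that structure nine comparisons give 29.4% at 0.5 and 13.7% at 0.9, so the choice matters little.

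**Step 3, only results favouring music.** Each test then has a 2.5% chance.

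- k = 9, independent: 1 − 0.975^9 = 1 − 0.796 = 0.204
- k = 9, simulated: 13.6% at ρ = 0.5 and 6.2% at ρ = 0.9

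The comparator is 2.5% for a single test, so the ratio runs from 6.2/2.5 = 2.5 to 20.4/2.5 = 8.2.

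**Step 4, the two remedies.** One pre-specified comparison at α = 0.05 restores 5%. Keeping nine with a Bonferroni correction needs 0.05/9 = 0.0056 each. The standardised difference detectable with 80% power is (z for α + z for power) × √(2/n):

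| n per group | one test at 0.05 | nine tests at 0.0056 |
|---|---|---|
| 60 | 0.51 | 0.66 |
| 80 | 0.44 | 0.57 |

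Naming one comparison therefore costs less than correcting for all of them.

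**The case against.** The best defence is the study's exploratory status. It is called a pilot and preliminary research, its aims are to explore, and its timeline ends with planning the next funding application. A controlled error rate matters less there than in a confirmatory trial. That stands, and it lowers the severity. It does not remove the point, because the protocol poses a yes/no question, plans significance tests, offers its results as evidence for using live music and, under Dissemination, expects a direct impact on practice.

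The second defence is that the nine tests and the 5% level are not in the protocol. That also stands. The listed paired tests and the missing-data rule could mean before-to-after analyses with few tests. One contrast per pain scale would give 1 − 0.95² = 9.75%. The figures above are a range over assumed readings, not a property of a stated plan.

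A reader might also infer three stronger things that the documents do not support:

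- **That distress is among the outcomes tested.** It is collected only as free text.
- **That the three measures are declared equal in rank.** The protocol is silent on rank, and heart rate is plainly an add-on that may be recorded as not available.
- **That there are ten comparisons, with a 40% error rate.** This counts the recruitment Wong-Baker score, which cannot show a benefit of music.

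**Conclusion.** The point holds in limited form. The protocol asks whether music decreases pain but does not say which pain measure, at which time, in which music-versus-control comparison, gives the answer.

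At an assumed two-sided 5%, the chance of at least one false positive is about 12% to 37% for nine comparisons and about 10% to 18.5% for four, depending on correlation. Counting only results in favour of music, nine comparisons give about 6% to 20%, against 2.5% for a single test. It is tempting to say flatly that a chance positive is several times likelier than 5%. That holds for many tests with low to moderate correlation, but the factor falls to about two for a few highly correlated tests.

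The calculation covers the pain scores and heart rate only, and assumes that the groups differ in nothing but the music. Allocation by day is a separate matter that naming an outcome does not cure. Severity is moderate: the gap should be closed, but this is a pilot.

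**What to change.** Before recruitment opens, add to the protocol:

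1. **One main between-group comparison.** A suitable choice is the research nurse's FLACC during the procedure, music versus control, adjusted for age and procedure type. FLACC is the only pain score that the protocol describes as suitable for all recruited ages, and the during phase matches the study title.
2. **The timing of the before-procedure FLACC relative to the music.** The protocol does not state it, and one question put to the music group asks about music's effect before the procedure. If the score is fixed as preceding the music, adjust for it as well. If not, leave it out of the model. The recruitment Wong-Baker score can serve as a baseline only from age 3.
3. **Wong-Baker during the procedure as first secondary outcome.** The FLACC rater can hear the music, so the child's own report is a needed check.
4. **All other measures and times as exploratory**, reported as estimates with 95% intervals.
5. **A sentence stating that the answer to the research question rests on the main comparison.**

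The cost is a few sentences and a decision on the timing of one score, which may mean redefining or moving that measurement. The downside is that an isolated result on another measure or time point can no longer carry the conclusion.

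### Controls come only from days without musicians, with no stated randomisation or matching of days and no approach rule for controls, so a pain difference cannot be attributed to music with confidence

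*Protocol*

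**What the plan says.** The allocation rule is in the Methods section of the protocol and is repeated under Recruitment. The "musicians will spend eight weeks, twelve hours per week in the ED" and "will aim to recruit all eligible children during that period". For the comparison, the text continues: "The same number of participants will be recruited to the control (no live music) group as a comparison", and this happens when the musicians are absent ("recruited to the control (no live music) group as a comparison, on days that the musicians are not in the department"). The estimate is 60 to 80 children per group, described as flexible because the study is a pilot.

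The Timeline gives one window, January to March 2019, for "Recruitment of participants to the study, both experimental (music) and control (non-music) groups". Eligibility criteria, the screening tool and standard care are common to both groups, and so is consent: "For inclusion in either group, a parent or legal guardian must be available to give consent, collected by the Research Nurse".

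The Research Question reads "Does live music decrease the pain and distress of patients undergoing a procedure within the paediatric emergency department". The section on the value of the study says that it "will therefore use a controlled experimental design to investigate the impact of using therapeutic live music". The aims are worded as exploration.

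**The concern.** The question is causal, and the comparison that answers it is music days against other days. The total musician time is given, but weekdays and clock hours are given for neither group. The text does not say how musician days are chosen, or that control sessions fall at comparable times. Whatever varies with day or hour in an emergency department (staffing, which of the listed procedures come in, which children attend) may then vary with group.

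A second route is selection. In music sessions the team aims for every eligible child. On other days it needs only to reach the same number, and no rule says which eligible children to approach. The day also reveals the group before a family is approached. If the controls enrolled are not typical of those eligible, the documents provide no record that would show it.

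The result could be an apparent benefit that is really a difference in case mix, or a real benefit hidden by one.

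**Working it through.** **Text check.** The whole protocol was read for each feature that would separate group from day.

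| Feature | Music group | Control group |
|---|---|---|
| Days | Musicians present; choice of days not described | Musicians absent |
| Weekdays, clock hours | Not stated (12 hours a week in total) | Not stated |
| Randomised, alternated or matched sessions | Not stated | Not stated |
| Whom to approach | Aim: all eligible | Not stated; filled to the same number |
| Calendar window | 8 weeks, within January to March 2019 | January to March 2019 |
| Eligibility, screening tool, consent, standard care | Common | Common |

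**How far the shared window helps.** January to March 2019 has 31 + 28 + 31 = 90 days. The musicians' period is 8 × 7 = 56 days. If the 8 weeks are consecutive, up to 90 − 56 = 34 days fall in weeks with no music at all, and controls may be drawn from them. This is a maximum: the Timeline also starts analysis in March, so recruitment may end earlier.

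**What is recorded.** Covariates that could be used for adjustment include age, gender, earlier experience of the procedure, hospital visits in the past 12 months, past upsetting experience, analgesia, clinician role and grade, baseline Wong-Baker score (age 3 and over only) and pre-procedure FLACC. They cover some of the possible differences. They do not describe eligible children who were never approached.

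**Size.** The 60 to 80 per group comes with no alpha, power, effect size or SD, so there is no power calculation to reproduce. The size and direction of any bias cannot be derived from the document. What can be shown is how sensitive a comparison of this size would be.

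Assumptions: two independent groups of n children, a standardised outcome, a normal approximation, a two-sided 5% test, no true effect of music, and an imbalance of δ SD between the groups.

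- Standard error: SE = √(2/n), which is 0.183 for n = 60 and 0.158 for n = 80.
- Half-width of the 95% interval: 1.96 × SE = 0.358 SD and 0.310 SD.
- Chance of a significant difference: P = Φ(δ/SE − 1.96) + Φ(−δ/SE − 1.96).

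| Assumed imbalance δ | n = 60 | n = 80 |
|---|---|---|
| 0.1 SD | 0.085 | 0.097 |
| 0.2 SD | 0.195 | 0.244 |
| 0.3 SD | 0.376 | 0.475 |

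The nominal value is 0.05. None of the three imbalances is taken from the protocol.

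**Feasibility of alternating weekdays.** If musicians come on k days a week, pairing each music weekday with a different control weekday in the same week needs 2k weekdays. With 7 in a week, k can be at most 3. Over 8 weeks each paired weekday then carries 8/2 = 4 music and 4 control sessions. The protocol does not state k.

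**The case against.** The strongest reply is that this is an openly described pilot. The protocol nowhere claims to be randomised, its aims are exploratory, and allocation by day is a practical choice when musicians attend for only 12 hours a week. Both groups share one department, one window, one screening tool and one consent process, and many covariates are recorded. Much of the criticism also rests on what the text leaves unsaid: no different approach rule is stated for controls, and hours or logs may sit in working documents. The analysis plan, which is not at hand, may specify adjustment.

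Most of this stands as a limit on the harm. It does not remove the point. Allocation and recruitment rules belong in the protocol. A later analysis plan can adjust for what was recorded, but it cannot create comparable sessions or recover who was eligible and not approached.

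Some stronger readings are tempting and are not supported:

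- *The groups do differ, or the bias favours music.* Nothing in the document shows either.
- *The days are known to be chosen non-randomly.* The protocol does not say how they are chosen; it only states no random method.
- *No difference could ever be attributed to music.* Partial adjustment is possible, so the loss is one of confidence.
- *The CRF omits date, start time and procedure type.* They are not in the list under Target population and sampling. But that list also omits FLACC, which the data collection section places on the CRF, and the Research Nurse may consult medical records. This is a question to confirm, not a defect.

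**Conclusion.** The point holds in this limited form. As written, group is confounded with calendar day, and possibly with hour, staffing, procedure mix and selection of control children. A between-group difference in pain therefore cannot be attributed to music with confidence.

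Its size is unknown. The illustration shows only that, at 60 to 80 per group, imbalances of 0.1 to 0.3 SD would raise the false-positive rate from 5% to between about 9% and 48%. That range rests wholly on assumed imbalances, independent children and an unadjusted comparison. It is not an estimate of the bias in this study.

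The matter should be fixed before recruitment, because the remedy is cheap then and partly out of reach afterwards. It does not make the pilot worthless: the qualitative data and the feasibility experience do not depend on this comparison in the same way.

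**What to change.** 1. **Timetable.** Before recruitment, set control sessions to cover the same weekdays and clock hours as music sessions, over the same weeks. Where musicians are available for both sessions of a pair, choose at random which one has music. Otherwise alternate: either between paired weekdays, reversing the roles each week (feasible up to three music days a week), or by swapping music and control weekdays from week to week as availability allows. The groups can stay on separate days.
2. **One approach rule.** In both groups, aim to approach every eligible child in each study session. Keep a log by group of children eligible, approached, declined and enrolled.
3. **Label and analysis.** If sessions are not randomised, describe the study as a non-randomised controlled pilot, compare the groups with adjustment for the recorded baseline covariates, and limit causal conclusions. Items recorded during the procedure, such as Entonox use or other distraction, may themselves respond to the music and should not be treated as baseline.

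As a query, confirm that date, start time and procedure type are captured somewhere usable.

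The cost is protocol wording, a timetable and a log. Scheduling of musicians and Research Nurses becomes less free, and random choice needs musicians available for both sessions of a pair. Approaching all eligible controls may leave the groups unequal in size. The 12 musician-hours a week for 8 weeks are unchanged.
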